6.6 Randomization

After patients have been found to be eligible for inclusion in the study and prior to TURBT the site will request randomization approval from the Medical Monitor. The patient must not undergo TURBT until they have been randomized.

A randomization scheme using permuted block design will be developed. An IVRS/IWRS system will be used to assign randomization ID once patients meet eligibility criteria and are ready to be randomized. The randomization code will be different than Patient ID that has been assigned to a patient and a mapping of randomization ID-Patient ID will be kept in a secured database.

6.7 Non-Study Treatments

6.7.1 Prior and Concomitant Medications

All medications administered from the time Informed Consent is signed until 35 days post TURBT will be recorded on the CRF. After 35 days, until patient is discontinued, only medications to treat NMIBC are to be recorded. Start and stop dates and reasons for medication use will be noted. Patients may use acetaminophen or antipyretics to manage side effects associated with TURBT and administration of study drug.

The Investigator may also prescribe standard post-operative medications.

6.7.2 Prohibited Medications

Following Day 1 treatment and prior to recurrence, patients in the Target Population should not receive other medications to treat bladder cancer. If a patient starts another therapy for bladder cancer during the follow-up period, the patient will be withdrawn from the study.

No diuretics are allowed prior to instillation on study drug instillation day. Patients should have at least a 7- to 10-day washout period for all anticoagulants, including low-dose aspirin.

7 SAFETY ASSESSMENT

7.1 Safety Measures

It is the responsibility of the Principal Investigator to oversee the safety of the subjects at their site and to report all AEs/SAEs that are observed or reported during the study, regardless of relationship to study drug or clinical significance.

Safety data will also be reviewed on a regular basis by Spectrum's study monitoring team, which includes a Clinical Research Associate (CRA), the Medical Monitor, and other personnel from the company or its designee.

Adverse events will be characterized by intensity (severity), causality, and seriousness by the Investigator based on the regulatory definitions included below.

This study will utilize the National Cancer Institute (NCI) Common Terminology Criteria for Adverse Events (CTCAE) Scale Version 4.03 for AE grading.

7.2 Adverse Events

An AE is defined as any untoward medical occurrence in a patient or clinical investigation patient, temporally associated with the use of a medicinal product or study procedure, whether or not considered related to the medicinal product. Therefore, an AE can be any unfavorable and unintended sign (including an abnormal laboratory finding), symptom, or disease (new or exacerbated) temporally associated with the use of a medicinal product. A treatment-emergent AE (TEAE) is any AE that occurs from the first dose of study treatment until 35 days after the last dose of study drug administration.

From the time the study Informed Consent is signed through the day of study drug administration, only SAEs that are related to study procedures are to be recorded. For all non-Target population patients, all adverse events from the time of study drug administration until Day 35 (± 5 days) post-TURBT will be recorded. For Target population patients, all adverse events will be recorded from the time of study drug administration until the 3-month Follow-up Visit. Only deaths and AEs related to study procedures will be recorded from the 3 month visit until the End-of-Study. The study will record all AEs according to the information in [Section 7.3](#).

Examples of AEs **include**:

- Exacerbation of a chronic or intermittent pre-existing condition including either an increase in frequency and/or intensity of the condition.
- New conditions detected or diagnosed after investigational product administration.
- Signs, symptoms, or the clinical sequelae of a suspected drug interaction.
- Signs, symptoms, or the clinical sequelae of a suspected overdose of either investigational product or a concurrent medication.
- AEs may include pre-treatment or post-treatment events that occur as a result of protocol-mandated procedures, ie, invasive procedures.

Abnormal laboratory results are to be recorded as AEs, if any of the following conditions are met:

- The abnormal laboratory value leads to a therapeutic intervention.
- The abnormal laboratory value is considered to be clinically significant by the Investigator.
- The abnormal laboratory value is predefined as an AE in the protocol or in another document communicated to the Investigator by Spectrum or designee.

Examples of events that **do not** constitute AEs include:

- Medical or surgical procedures (eg, endoscopy, appendectomy); the condition that leads to the procedure is an AE.

- Situations where an untoward medical occurrence does not occur (eg, social and/or convenience admission to a hospital).
- Anticipated day-to-day fluctuations of pre-existing disease(s) or condition(s) present or detected at the start of the study that do not worsen.
- Planned and prescheduled hospitalizations and procedures.
- Progressive disease.

7.3 Guidelines for Recording and Attribution Scoring of Adverse Events

Timely and complete reporting of all AEs is required for all patients. Monitoring and documentation of all AEs allows for identification of potential study-drug or dose-related AEs, and for adherence to regulatory requirements. Please refer to the CRF Completion Guidelines located in the study binder for detailed instructions for AE reporting.

7.3.1 Recording of Adverse Events

From the time the study Informed Consent is signed through the day of study drug administration, only SAEs that are related to study procedures are to be recorded. For all non-Target population patients, all adverse events from the time of study drug administration until Day 35 (± 5 days) post-TURBT will be recorded. For Target population patients, all adverse events will be recorded from the time of study drug administration until the 3-month Follow-up Visit. Only AEs related to study procedures and deaths will be recorded from the 3 month visit until a recurrence or the remainder of the follow-up period, whichever comes first.

All AEs should include resolution at the End-of-Study for a patient. The following conventions should be followed when patient completes or discontinues from the study

- If a patient dies, the date of death should be the date of AE stop for all ongoing AEs at the time of death.
- If a patient discontinues study drug due to an AE(s), the outcome of the AE is to be followed for 35 days (± 5 days) from the date of discontinuation or until the AE has returned to Grade ≤ 1 or returned to baseline conditions for the patient.

The status of the AE and the date of last contact with the patient will be captured. If the AE has not returned to Grade ≤ 1 or to Baseline conditions for the patient by the End-of-Study, the AE stop date should be left as ongoing.

All AEs will be classified by intensity/severity ([Section 7.3.2](#)), relationship to study drug ([Section 7.5](#)), and as serious or nonserious ([Section 7.7](#)).

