Once randomized, patients will undergo TURBT on Day 1 and the study drug instillation will occur at 60 ± 30 minutes post-TURBT and will be retained for 60 minutes (± 5 minutes) in the bladder. All histology specimens will be reviewed by a local pathology laboratory and all clinical treatment decisions will be based on the local pathology review. Patient target disease will be confirmed and efficacy analyses will be performed based on the pathology results. The target study population is low- to intermediate-risk patients who have Ta histology, including PUNLMP, as confirmed by a pathology laboratory. Patients whose tumor histology does not meet the criteria for eligibility, as confirmed by pathology (Non-Target Population), will be followed up for safety on Day 35 (± 5 days) (Safety Follow-up Visit) and will then be discontinued from the study. If the pathology results are delayed beyond 35 days, the Safety Follow-up Visit will be conducted when the results are available for these patients.

Patients who have pathology confirmed target histology will not receive additional treatment for NMIBC during the follow-up prior to recurrence. All patients will be followed until either a confirmed tumor recurrence or the End-of-Study, whichever occurs first.

The primary analysis will be conducted once the required number of recurrence events are observed as detailed in the Statistical Methods below. The number of events needed to perform the final primary endpoint analysis was estimated based on the recurrence rate at 24 months from previous studies. The follow-up schedule is below:

- Cystoscopic examination and urine cytology every 3 months (± 30 days) (calculated from date of TURBT) for 2 years for tumor recurrence and progression and then every 6 months (± 60 days) until either a confirmed tumor recurrence or the End-of-Study, whichever occurs first.
- If at any time during the study there is a histologically confirmed tumor recurrence, the patient will be discontinued from the study at that time and may then be treated per the Investigator's standard of care.

The study will end (End-of-Study) when the required number of events for the primary endpoint analysis are accrued.

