4.3 Patient Discontinuation/Withdrawal Criteria

Patients can withdraw from participation in this study at any time, for any reason, specified or unspecified, and without prejudice.

Patients must be withdrawn from study participation for the following reasons:

[figure not shown]
- It is determined by Day 1 pathology review that the patient has histology other than low-to intermediate-risk NMIBC
- Development of an adverse event (AE) that interferes with the patient's participation
- Patient withdrawal of informed consent
- Investigator decision
- Sponsor decision
- The patient refuses further follow-up study procedures, including cystoscopy
- The patient is lost to follow-up (missed at least two consecutive follow-up cystoscopies)
- Patient has a cystectomy
- Patient has a histologically-confirmed recurrence
- Death
- Pregnancy

The reason for the patient discontinuing study treatment or terminating from the study must be recorded on the case report form (CRF). For patients who discontinue from the study during the follow-up period or who are withdrawn, the date of last contact will be the final visit.

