5.4.10 Adverse Event

At every visit, the Investigator or designee will question the patient about adverse events and intercurrent illnesses since the last visit, according to the National Cancer Institute (NCI) Common Terminology Criteria for Adverse Events (CTCAE) Version 4.03 for AE grading, and will record the pertinent information on the CRF.

From the time the study Informed Consent is signed through the day of study drug administration, only SAEs that are related to study procedures are to be recorded. For all non-Target population patients, all adverse events from the time of study drug administration until Day 35 (± 5 days) post-TURBT will be recorded. For Target population patients, all adverse events will be recorded from the time of study drug administration until the 3-month Follow-up Visit. Only deaths and AEs related to study procedures will be recorded from the 3 month visit until the End-of-Study.

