8.6.1.2 Deaths

All deaths reported during the study will be tabulated and summarized by treatment arm.

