4 STATISTICAL CONSIDERATIONS

4.1 General Analysis Considerations

The statistical analyses will be reported using summary tables, figures, and data listings. All analyses and tabulations will be performed using SAS[®] Version 9.4 or higher. All tables, listings, and figures will be validated and reviewed before being finalized. Tables will be reviewed for accuracy, consistency with this plan, consistency within tables, and consistency with corresponding output.

For the continuous variables, number of non-missing values and mean, standard deviation, median, minimum, and maximum will be tabulated by treatment arm. For the categorical variables, the counts and percent for each possible value will be tabulated by treatment arm.

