7.3.3 Serious Adverse Events

Serious adverse events are those events that result in death, are life-threatening, require or prolong inpatient hospitalization, result in persistent or significant disability/incapacity, or cause congenital anomaly/birth defect.

All SAEs will be provided in listing and the incidence will be summarized in the overall summary of TEAE table.

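### Deaths and procedure-related events after Month 3 are in practice observed only until recurrence, so crude by-arm summaries rest on unequal observation time (about 1.15 to 1 under the planning assumptions) and should be shown with patient-year rates

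*Protocol*

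**What the plan says.** **When recording stops.** Protocol 7.3.1 limits late recording to procedure-related AEs and deaths, and closes the window at recurrence: "deaths will be recorded from the 3 month visit until a recurrence or the remainder of the follow-up period, whichever comes first". Protocol 5.4.10 words it differently: "Only deaths and AEs related to study procedures will be recorded from the 3 month visit until the End-of-Study". Section 7.2 and footnote j of the assessment schedule also run to End-of-Study. The synopsis and section 7.7.1 refer to the rest of the follow-up period. Only 7.3.1 names recurrence.

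**When the patient leaves.** Protocol 3.1 says that at confirmed recurrence "the patient will be discontinued from the study at that time". Protocol 4.3 lists "Patient has a histologically-confirmed recurrence" among the mandatory reasons for withdrawal.

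**How late harms are summarized.** Protocol 8.6.1.2: "All deaths reported during the study will be tabulated and summarized by treatment arm". Protocol 8.6.2 tabulates SAEs by preferred term and arm. SAP 4.1: "For the categorical variables, the counts and percent for each possible value will be tabulated by treatment arm". SAP 7.3.3: "All SAEs will be provided in listing and the incidence will be summarized in the overall summary of TEAE table". SAP 7.3.4 covers only TEAEs leading to death, and a TEAE ends 35 days after dosing (SAP 7.3.1). Deaths nevertheless remain an endpoint without a time limit in SAP 3.4.2. SAP 7.1 defines exposure by instillation time, volume and retention. Neither document uses time under observation as a denominator for any harm.

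**The concern.** The stopping rule reads the same for both arms but gives them different observation times if the drug works. Recurrence is the primary efficacy outcome, and the design assumes that its hazard is 35% lower on Qapzola. Placebo patients would then leave sooner, and a death or procedure-related event after they leave is not counted. Qapzola patients stay longer and undergo more protocol cystoscopies, so they have more opportunity for a procedure-related event.

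A crude percentage compares arms fairly only if both are watched for similar times. Here a late-harm percentage mixes the event rate with the effect on recurrence. It leans against Qapzola if recurrence is delayed and in its favor if recurrence is hastened. This matters because safety is the only objective left in the SAP (section 2.1).

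**Working it through.** **Inputs.** Protocol 8.1 gives a placebo hazard of 0.3, HR 0.65 (so 0.3 × 0.65 = 0.195 on Qapzola), 24 months accrual plus 24 months follow-up, 284 and 141 Target patients, and 208 events. Protocol 1.3.2 reports fatal AEs in about 3% of patients in the earlier Phase 3 studies, which lasted about 2 years. SAP 3.3 says that nobody was followed beyond 24 months.

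**Assumptions.** Hazards are annual (the unit is not stated), recurrence times exponential, accrual uniform (potential follow-up T uniform on 2 to 4 years), and there is no dropout.

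**Step 1: reproduce the plan's figure.** The probability of no recurrence, averaged over T, is (e^(−2h) − e^(−4h)) / (2h).
- Placebo: (0.5488 − 0.3012) / 0.6 = 0.4127, so 141 × 0.5873 = 82.8 events.
- Qapzola: (0.6771 − 0.4584) / 0.39 = 0.5606, so 284 × 0.4394 = 124.8 events.
- Total: 207.6, against 208 stated.

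A fixed 24 months would give 155 events, and the 2.5 + 2.5 years of Protocol 3.2 would give 240. The 2-to-4-year model is therefore the one behind the plan.

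**Step 2: mean observed time to recurrence or end of study.** This is the average of (1 − e^(−hT)) / h.
- Placebo: 0.5873 / 0.3 = 1.958 years.
- Qapzola: 0.4394 / 0.195 = 2.253 years.
- Ratio: 1.151.

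After Month 3, the numerator is e^(−0.25h) minus the average from Step 1.
- Placebo: (0.9277 − 0.4127) / 0.3 = 1.717 years.
- Qapzola: (0.9524 − 0.5606) / 0.195 = 2.009 years.
- Ratio: 1.170.

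**Step 3: other cases (Qapzola / placebo observation time).**

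| Case | From instillation | After Month 3 |
|---|---|---|
| 2 to 4 years, HR 0.65 | 1.151 | 1.170 |
| Same, recurrence found only at scheduled visits (simulated) | 1.134 | 1.153 |
| 2 to 4 years, HR 0.79 (pooled earlier studies, Protocol 1.3.1.2) | 1.087 | 1.098 |
| 2 to 4 years, HR 1.0 | 1.000 | 1.000 |
| 24 months for every patient, HR 0.65 | 1.101 | 1.118 |
| Spread evenly over 0 to 24 months, HR 0.65 | 1.067 | 1.087 |

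For the early windows at HR 0.65, the ratio is 1.005 over the first 35 days and 1.013 over the first 3 months.

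**Step 4: effect on crude deaths.** Assume the same death hazard in both arms, matching 3% in 2 years: d = −ln(0.97) / 2 = 0.0152 per year. The proportion dying while observed is d/(d + h) × [1 − average of e^(−(d+h)T)].
- Qapzola: 3.36% (9.5 of 284).
- Placebo: 2.92% (4.1 of 141).
- Ratio 1.149; difference 0.44 points.

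The ratio stays at about 1.15 for death rates from 1% to 2% per year. With 24 months for every patient, the proportions are 2.49% and 2.26%. For a late event with 10% risk in 2 years, the planned design gives 11.0% and 9.6%.

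**Step 5: the same deaths as rates.** Expected deaths divided by expected observed years equals d in each arm, about 1.52 per 100 patient-years. The rate ratio is 1.00.

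**The case against.** **The main harm tables are sound.** TEAEs run to 35 days, and full AE collection runs to Month 3 in Target patients and Day 35 in others. Observation in these windows differs by about 1% or less. A reader might infer that harms in general are distorted; the documents do not support that. This objection stands, and the point covers only deaths and late procedure-related events.

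**The effect is conditional and small.** A reader might also infer that the trial will show excess harm on Qapzola where none exists. That goes too far. The imbalance arises only if the drug delays recurrence, and no safety hypothesis test is planned. In simulation of the full design, a nominally significant excess of deaths on Qapzola occurred about 3% of the time, against 2.2% with no recurrence effect. For the 10% late event it was about 6%. What remains is a predictable lean in a descriptive comparison.

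**The SAP supersedes the protocol's analyses, and the trial stopped early.** This largely stands for deaths: SAP 7.3.4 counts only fatal TEAEs, so a late death does not enter that incidence. The figure of 1.15 belongs to the planned design, not to the terminated trial. Two openings remain. SAP 7.3.3 takes in every SAE without a time limit, so late procedure-related SAEs may enter the crude incidence. Deaths also stay in the endpoint list with no specified summary of all deaths.

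**Most sections say recording runs to End-of-Study.** Withdrawal at recurrence makes the practical result much the same, because no further study visit is scheduled at which an event would be elicited. The wording conflict is nevertheless real.

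**Conclusion.** The point holds for deaths and for procedure-related AEs and SAEs after Month 3. In practice their observation ends at recurrence, and the planned summaries ignore time at risk. At the planned HR of 0.65, observation is about 1.15 times as long on Qapzola (1.17 after Month 3), or about 1.13 and 1.15 if recurrence is found only at scheduled visits. With equal true hazards, crude death proportions would differ by roughly 0.4 percentage points. In the terminated trial the ratio at HR 0.65 is at most about 1.10 (1.12 after Month 3), and about 1.07 if follow-up was spread evenly over 0 to 24 months. There it bears mainly on late SAEs and on any by-arm summary of all deaths.

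These sizes rest on annual exponential hazards, uniform accrual, no dropout and, for deaths, an assumed common hazard taken from the earlier studies. This is a low-cost improvement to reporting, not a defect that invalidates the safety evaluation.

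**What to change.** - In Protocol 8.6.1.2 and 8.6.2, in SAP 7.3.3, and in any SAP summary of all deaths, show total and mean observation time by actual arm. Beside the crude counts, add events per 100 patient-years with 95% CI for deaths and for procedure-related AEs and SAEs after Month 3. Time at risk runs from instillation (from Month 3 for the late events) to the earliest of event, recurrence or other withdrawal, and End-of-Study.
- Leave the 35-day TEAE tables as crude incidences.
- Reconcile Protocol 7.3.1 (until recurrence) with 5.4.10, 7.2 and schedule footnote j (until End-of-Study), and with the synopsis and 7.7.1 (rest of follow-up).

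**Cost.** SAP wording and an extra column or short table, built from dates already collected (instillation, recurrence, last contact, death). No new patients or visits are needed.

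**Limits.** The rates assume a roughly constant hazard and will be imprecise with few events. They still stop at recurrence, so they correct the unequal person-time but not any bias that arises if recurrence itself predicts death.

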7.3.2 Grading of Adverse Events

This study will utilize the NCI CTCAE Version 4.03 for AE grading.

7.4 Follow-up of Adverse Events

All AEs and significant abnormal laboratory values are to be followed up in accordance with the International Conference on Harmonization (ICH) Good Clinical Practice (GCP) guidelines, and other applicable regulatory requirements (eg, United States [US] Code of Federal Regulations [CFR]).

7.5 Relationship

The Investigator must make a causality assessment and document their assessment as to the relationship of all AEs and SAEs to study treatment for up to 35 days (± 5 days) after treatment (Table 3).

Table 3 Investigator Assessment of Adverse Event Causality

Relationship	Description
Not Related	The event is clearly related to factors other than study treatment, such as the patient’s clinical state, therapeutic interventions, or concomitant medications administered to the patient.
Unlikely Related	The temporal association, patient history and/or circumstances are such that the study drug or treatment is not likely to have had an association with observed event.
Possibly Related	The event follows a reasonable temporal sequence from the time of study treatment administration, and/or follows a known response pattern to study treatment, but could have been produced by other factors, such as the patient’s clinical state, therapeutic interventions, or concomitant medications administered to the patient.
Probably Related	The event follows a reasonable temporal sequence from the time of study treatment administration, and follows a known response pattern to study treatment, and cannot be reasonably explained by other factors, such as the patient’s clinical state, therapeutic interventions, or concomitant medications administered to the patient.
Definitely Related	The event follows a reasonable temporal sequence from the time of study treatment administration, and follows a known response pattern to study treatment, and cannot be reasonably explained by other factors, such as the patient’s clinical state, therapeutic interventions, or concomitant medications administered to the patient. In addition, the event either occurs immediately following study treatment administration, improves on stopping study treatment, reappears on repeat exposure, or there is a positive reaction at the application site.

